4.1.1 Phase 1 Dose Escalation: Melanoma (*COMPLETE*)

The Phase 1 will consist of up to 4 Dose Escalation cohorts to evaluate the safety and tolerability of SD-101 given in combination with pembrolizumab in melanoma populations (anti-PD-1/L1 naïve and anti-PD-1/L1 experienced with progressive disease) to identify an RP2D to be evaluated in Phase 2.

Phase 1 employs a modified 3 + 3 study design, evaluating escalating or intermediate dose levels of SD-101 (given with a fixed dose of pembrolizumab) in patients with metastatic melanoma. Cohorts of 3 to 6 patients will be enrolled at each dose level, and each patient will participate in only 1 cohort. Patients at each dose level will be treated and observed for dose-limiting toxicities (DLTs) through the DLT assessment period (Study Day 1-29). Once an RP2D is declared, an additional 6 patients may be enrolled to assess safety at this dose.

Patients in Escalation Cohorts 1-4 will be administered 2.0 mg, 4.0 mg, 8.0 mg, and 1.0 mg, respectively, of SD-101 in combination with 200 mg pembrolizumab Q3W per the Schedule of Trial Events.

The melanoma Dose Escalation cohorts, patient populations, and treatment assignments are outlined in Table 4-2.

Table 4-2: Phase 1 Melanoma Dose Escalation Cohorts (*COMPLETE*)

Cohort	Anti-PD-1/L1 Experience	SD-101 Dose	n	Dosing Schema ^a
1	Naïve or experienced	2.0 mg per lesion in 1 injectable lesion (Lesion A)	3 - 6	A
2	Naïve or experienced	4.0 mg per lesion in 1 injectable lesion (Lesion A)	3 - 6	A
3	Naïve or experienced	8.0 mg per lesion in 1 injectable lesion (Lesion A)	3 - 6	A
4	Naïve or experienced	1.0 mg per lesion in 1 injectable lesion (Lesion A)	3 - 6	A ^b

Anti-PD-1/L1 = anti-programmed death receptor-1/ligand 1.

^a Dosing Schema:

A: SD-101 and pembrolizumab dosing both start on Day 1 and patients receive 1 course of SD-101 (4 weekly doses and then every 3 weeks on schedule with pembrolizumab for 7 additional doses).

^b 1.0 mg was added at Protocol Amendment 4.

[figure not shown]
4.1.1.1 Dosing Schedule (*COMPLETE*)

Phase 1 portion of this trial is a Dose Escalation of SD-101 with a fixed dose of pembrolizumab as depicted in Figure 4-2. SD-101 will be administered intratumorally as 4 weekly doses

followed by 1 dose Q3W for 7 additional doses. Pembrolizumab 200 mg will be administered intravenously Q3W starting on Day 1 for up to 35 treatments (approximately 2 years) or until disease progression. SD-101 will be administered before pembrolizumab on days when both drugs are scheduled to be used.

Figure 4-2: Trial Flow Diagram for Phase 1 Dose Escalation Cohorts 1 to 4 (COMPLETE)

4.1.1.2 DLT Assessment (COMPLETE)

Cohorts of 3 to 6 patients will be enrolled at each dose level, and each patient will participate in only 1 cohort. Patients at each dose level will be treated and observed for DLT through the DLT assessment period (Study Day 1-29). In addition to use of a modified 3 + 3 Dose Escalation design to assess a maximum tolerated dose (MTD), Phase 1 implements a staggered enrollment for a cohort. Patients enrolled under staggered enrollment in Phase 1 are referred to as sentinel patients in the protocol. The starting dose of SD-101 will be 2.0 mg administered intratumorally and will be given to 1 sentinel patient. If the sentinel patient does not experience a DLT within

72 hours, the second patient in the cohort may be dosed. If no DLT is experienced in the second patient after 72 hours, the third patient (and up to 3 additional patients) may be dosed. If a DLT is experienced in the first sentinel patient within 72 hours of injection, a second sentinel patient may be dosed with SD-101 following a safety review by the Safety Review Team (comprised of the Dynavax Medical Monitor, Phase 1 coordinating investigator, and other key safety Dynavax personnel as described in the Cohort Safety Review Plan) and an evaluation of *safe to proceed*. If no DLT is observed after 72 hours in the second sentinel patient, the third and subsequent patients in the cohort may be enrolled.

If there is no DLT observed (Section 9.1) in the group of 3 or more patients, the next cohort will be enrolled, and escalation will proceed to the next highest dose with a sentinel patient receiving SD-101 at least 72 hours prior to dosing of subsequent patients.

If a DLT is observed in 1 patient in the first 3 patients enrolled in a cohort, enrollment will proceed and the cohort size will be increased up to 6 patients. If only 1 DLT is observed in 6 patients in a cohort, escalation will proceed, and the next cohort may begin enrollment.

A minimum of 3 patients will be enrolled in each Cohort. Dose escalation will proceed if no DLT is observed in all patients enrolled. If 1 DLT is observed in any cohort after 3 patients have been enrolled, the cohort size will be increased to 6 patients. The maximum allowed DLTs per cohort to allow subsequent Dose Escalation is 1 DLT observed in 6 patients. The sponsor may also choose to enroll up to 6 patients initially into a cohort. Dose escalation will proceed if no more than 1 DLT is observed in 6 patients.

If only 1 DLT is observed in 6 patients in a cohort, escalation will proceed and the next cohort may begin enrollment.

If ≥ 2 of 6 patients experience a DLT in any cohort, Dose Escalation will cease and the previous lower dose of SD-101 may be designated the MTD. However, the sponsor may also decide to investigate an additional lower or intermediate dose cohort(s) than have already been tested. Patients will be enrolled and evaluated as described above for previous Dose Escalation cohorts except that staggered enrollment with a sentinel patient will not be required. Three to 6 patients will be enrolled at the intermediate or lower dose and DLT assessments performed, with expansion to 6 patients as required and applicable. A maximum of 0 DLTs in the first 3 patients or 1 DLT in the first 6 patients will define this dose as the MTD.

The planned dose cohorts for SD-101 are 2.0 mg, 4.0 mg, and 8.0 mg. Dose Escalation will continue until an MTD is determined or a maximum planned dose (ie, a total body dose of 8.0 mg) is reached. In addition, a 1.0 mg dose cohort, added in Amendment 4 of this protocol, will not require staggered enrollment with a sentinel patient as long as any higher dose cohort

has completed the DLT assessment period and met protocol criteria for Dose Escalation as described in this section. Decisions to escalate the dose of SD-101 to the next highest level will be based on review of safety data from the time of the first injection (Day 1) through Day 29 (the DLT assessment period). If 1 DLT in 6 patients or 2 Grade 2 AEs considered drug-related (except for malaise, headache, myalgia, fatigue, or chills) occur in 3 patients in a dose cohort, the Dose Escalation increment for the next dosing cohort will be decreased from 100% to 50%. Intra-patient Dose Escalation is not permitted.

The RP2D of SD-101 given in combination with pembrolizumab will be chosen based on all available data including efficacy, safety, and pharmacodynamic biomarkers (eg, IFN-inducible gene signature and tumor-infiltrating lymphocytes). The RP2D will not exceed the MTD.

Disease response and study treatment management for Dose Escalation will be assessed by the investigator based on RECIST v1.1 and immune-related Response Evaluation Criteria In Solid Tumors (irRECIST) (ie, scans obtained at least 4 weeks later that qualify as PD per RECIST v1.1 [Appendix 6]). This assessment of disease response and progression is consistent with current pembrolizumab studies and is implemented due to observed *pseudoprogression* as well as late responses with immunotherapy. The protocol also allows patients who are clinically stable and have unconfirmed PD to continue on pembrolizumab and SD-101 per investigator decision. All patients who develop confirmed progressive disease must discontinue all study treatment unless requested by an investigator and approved by a Dynavax Medical Monitor. Patients who discontinue pembrolizumab must discontinue SD-101. Pembrolizumab may be continued as a single agent if SD-101 is discontinued per investigator decision as described in Section 9.2.

4.1.2 Phase 2 Dose Expansion – Cohorts (*CLOSED*)

NOTE: As of Amendment 9, enrollment in Phase 2 of the trial is closed. Enrolled patients should continue receiving their assigned treatment per protocol.

4.1.2.1 Melanoma Cohorts

Melanoma Dose Expansion cohorts in Phase 2 will be treated with 8.0 mg or 2.0 mg of SD-101 from Phase 1 in combination with 200 mg pembrolizumab Q3W.

For metastatic melanoma, planned enrollment is approximately 60 patients in Expansion Cohort 1 and approximately 25 each in Expansion Cohort 2 and Cohort 5, and approximately 50 in Cohort 8. Patients in Cohort 2 will have had disease progression on anti-PD-1/L1 therapy, those in Cohort 8 will have had refractory or resistant response to anti-PD-1/L1 therapy, and patients in Cohorts 1 and 5 will be naïve to anti-PD-1/L1 therapy.

The melanoma expansion cohorts, patient populations, and treatment assignments are outlined in [Table 4-3](#).

Table 4-3: Phase 2 Melanoma Dose Expansion Cohorts (CLOSED)

Cohort	Anti-PD-1/L1 Experience	SD-101 Dose	n	Dosing Schema ^a
1	Naïve	8.0 mg in a single injectable lesion if 1 lesion is selected (Lesion A) or 2.0 mg per lesion if 2 to 4 lesions are selected for injection (Lesion A, Lesion B, Lesion C, Lesion D)	Approximately 60	B
2	Experienced ^b	8.0 mg in a single injectable lesion (Lesion A)	Approximately 25	A
5	Naïve	2.0 mg per lesion in 1 to 4 injectable lesions (Lesion A, Lesion B, Lesion C, Lesion D)	Approximately 25	A1
8	Refractory or resistant ^c	2.0 mg in 1 ml per injection in 1 to 4 separate lesions for lesions measuring up to 5 cm in the longest diameter; or for lesions larger than 5 cm, 2.0 mg in 1 ml per injection in 1 to 4 separate regions where the injections are \geq 5 cm apart (maximum total dose is 8.0 mg)	Approximately 50	A1

Anti-PD-1/L1 = anti-programmed death receptor-1/ligand 1.

^a Dosing Schema:

A: SD-101 and pembrolizumab dosing both start on Day 1 and patients receive 2 courses of SD-101 (each course, separated by 9 weeks, is 4 weekly doses and then every 3 weeks on schedule with pembrolizumab for 7 additional doses)

B: SD-101 dosing starts on Day 22 at the second dose of pembrolizumab and patients receive 2 courses of SD-101 (each course, separated by 9 weeks, is 4 weekly doses and then every 3 weeks on schedule with pembrolizumab for 7 additional doses)

A1: SD-101 and pembrolizumab dosing both start on Day 1 and patients receive 1 course of SD-101 (4 weekly then every 3 weeks on schedule with pembrolizumab up to Week 51)

^b Received prior treatment regimen containing an anti-PD-1/L1 drug.

^c Received at least 2 doses of an anti-PD-1/L1 therapy and experienced PD within 3 months after last dose of anti-PD-1/L1 therapy. Anti-PD-1/L1 refractory or resistant patients must have documented PD per RECIST v.1.1, which has been confirmed by a second scan at least 4 weeks from the date of the first documented PD, in the absence of rapid clinical progression.

4.1.2.2 HNSCC Cohorts

HNSCC Dose Expansion cohorts in Phase 2 will be treated with the selected RP2D (8.0 mg or 2.0 mg of SD-101) from Phase 1 in combination with 200 mg pembrolizumab Q3W.

In Phase 2 HNSCC, approximately 25 anti-PD-1/L1 naïve patients in each of Expansion Cohorts 3 and 6, and approximately 25 patients who have disease progression on anti-PD-1/L1 therapy in each of Expansion Cohorts 4 and 7 will be enrolled.

The HNSCC Dose Expansion cohorts, patient populations, and treatment assignments are outlined in [Table 4-4](#).

Table 4-4: Phase 2 HNSCC Dose Expansion (CLOSED)

Cohort	Anti-PD-1/L1 Experience	SD-101 Dose	n	Dosing Schema ^a
3	Naïve	8.0 mg in a single injectable lesion (Lesion A) ^b	Approximately 25	B
4	Experienced ^c	8.0 mg in a single injectable lesion (Lesion A) ^b	Approximately 25	A
6	Naïve	2.0 mg per lesion in 1 to 4 injectable lesions (Lesion A, Lesion B, Lesion C, Lesion D)	Approximately 25	A1
7	Refractory or resistant ^d	2.0 mg per lesion in 1 to 4 injectable lesions (Lesion A, Lesion B, Lesion C, Lesion D)	Approximately 25	A1

Anti-PD-1/L1 = anti-programmed death receptor-1/ligand 1.

^a Dosing Schema:

A: SD-101 and pembrolizumab dosing both start on Day 1 and patients receive 2 courses of SD-101 (each course, separated by 9 weeks, is 4 weekly doses and then every 3 weeks on schedule with pembrolizumab for 7 additional doses)

B: SD-101 dosing starts on Day 22 at the second dose of pembrolizumab and patients receive 2 courses of SD-101 (each course, separated by 9 weeks, is 4 weekly doses and then every 3 weeks on schedule with pembrolizumab for 7 additional doses)

A1: SD-101 and pembrolizumab dosing both start on Day 1 and patients receive 1 course of SD-101 (4 weekly then every 3 weeks on schedule with pembrolizumab up to Week 51)

^b Patients will receive 8.0 mg per lesion in 1 lesion with the option of injecting into up to 4 regions within the lesion in approximate equally divided volumes of an 8.0 mg dose.

^c Received prior treatment regimen containing an anti-PD-1/L1 drug.

^d Received at least 2 doses of an anti-PD-1/L1 therapy, where the last dose of anti-PD-1/L1 therapy was within 6 months of study enrollment (Day 1) and have either refractory response (PD occurred within 3 months duration of the start of treatment on anti-PD-1/L1 therapy) OR resistant response (PD occurred beyond 3 months duration of treatment on anti-PD-1/L1 therapy and within 6 months after the last dose of treatment on anti-PD-1/L1 therapy). Anti-PD-1/L1 refractory or resistant patients must have documented PD per RECIST v.1.1, which has been confirmed by a second scan at least 4 weeks from the date of the first documented PD, in the absence of rapid clinical progression.

4.1.3 Phase 2 Dose Expansion – Dosing Schedule

As presented in the Trial Flow Diagrams for the Dose Expansion Cohorts 1 to 4, patients with metastatic melanoma or HNSCC will receive 2 courses of the SD-101 dose regimen, with 9 weeks off between the 2 courses. In Cohorts 1 and 3 ([Figure 4-3](#)), patients will have a lead-in dose of pembrolizumab at Day 1 and start the treatment course on Day 22; whereas, in Cohorts 2 and 4 ([Figure 4-4](#)), SD-101 and pembrolizumab treatments will both start on Day 1. Metastatic melanoma or HNSCC patients in Cohorts 5, 6, 7, and 8 ([Figure 4-5](#)) will receive 1 course of SD-101 and dosing with SD-101 and pembrolizumab both start on Day 1. Pembrolizumab 200 mg will be administered intravenously Q3W until disease progression or up to 2 years. SD-101 will be administered before pembrolizumab on days when both drugs are scheduled to be used.

Figure 4-3: Trial Flow Diagram for Dose Expansion Cohorts 1 and 3 (CLOSED)

[figure not shown]

Figure 4-4: Trial Flow Diagram for Dose Expansion Cohorts 2 and 4 (CLOSED)

[figure not shown]
[figure not shown]

Figure 4-5: Trial Flow Diagram for Dose Expansion Cohorts 5, 6, 7, and 8 (CLOSED)

4.1.4 Phase 1 and Phase 2 – Assessments

NOTE: As of Amendment 9, Phase 1 of the trial is complete and enrollment in Phase 2 is closed. Phase 2 of the trial has been modified to continue dosing per protocol. The trial will stop collecting all efficacy endpoints. Assessments of disease response should be made per Investigator based on local standard of care and assessment guidelines. This section has been modified accordingly.

All patients will undergo safety assessments, pharmacodynamic assessments, tumor response assessments, and tumor biopsies performed at specified trial visits, as indicated in the Schedule of Trial Events ([Appendix 1](#) through [Appendix 4](#)).

Once informed consent is obtained, disease assessments prior to treatment will include:

- Complete physical examination including assessment of superficial lesions with photographic documentation and measurement of these lesions

- Radiographic imaging including computed tomography (CT) or magnetic resonance imaging (MRI) scans of the chest, abdomen, pelvis, brain, and other areas ([Appendix 7](#)), as clinically indicated. CT imaging is preferred. In addition, screening imaging for HNSCC patients requires imaging of the neck. The screening radiographic imaging will serve as baseline and must be obtained within 4 weeks of study enrollment, ie, receiving the first trial treatment.
- Laboratory assessments
- Baseline confirmation of PD-L1 expression from a biopsy of the target lesion (Lesion A) that will be injected with SD-101 in Phase 2 Expansion patients. A baseline biopsy should be collected within 28 days prior to the initiation of study treatment. Archival tissue of the target lesion within 3 months of screening is acceptable.
- Copy of pathology report confirming diagnosis

Disease assessment will include physical examination, photographic documentation and measurement of superficial lesions, and radiographic imaging ([Appendix 7](#)) with CT or MRI (with preference for CT) scans.

Repeat tumor biopsies will be conducted for all Cohorts. Biopsies of the target lesion (Lesion A) which has been injected with SD-101 are required at the time points as outlined in the Schedule of Trial Events ([Appendix 1](#) through [Appendix 4](#)). At each biopsy collection time point, 2 tissue biopsy samples will be collected per the study laboratory manual. Lesion A should be of a sufficient size such that the intratumoral biopsy does not compromise the investigator's ability to assess the lesion size changes per Response Evaluation Criteria in Solid Tumors (RECIST) over time. Biopsies from Lesion A are required. Additional biopsies from other injected lesions are optional, but strongly encouraged. Of note, 1 to 3 additional biopsies may be collected from other injected lesions if a cohort allows for injecting up to 4 lesions. Separate and additional biopsies from a non-injected lesion are also optional but strongly encouraged. If Lesion A or other biopsied lesions have regressed, further biopsies are not required. If an injected lesion has completely regressed, and there is no other replacement lesion (Section [6.2.2.2](#)), SD-101 will be injected peritumorally for up to the next 3 doses of SD-101. Further details on tumor biopsies are in Section [10.1.2](#).

In Phase 1, response will be assessed by evaluating Lesion A, all sites of disease outside Lesion A, and all lesions combined. In Phase 2, response will be assessed by evaluating all lesions injected with SD-101, lesion(s) not injected with SD-101, and all lesions combined.

Disease response and study treatment management for Dose Expansion will be assessed by the investigator based on RECIST v1.1 and irRECIST (ie, scans obtained at least 4 weeks later that qualify as PD per RECIST v1.1 [[Appendix 6](#)]). This assessment of disease response and progression is consistent with current pembrolizumab studies and was implemented due to

observed *pseudoprogression* as well as late responses with immunotherapy. The protocol also allows patients who are clinically stable and have unconfirmed PD to continue pembrolizumab and SD-101 per investigator decision and Dynavax Medical Monitor approval. All patients who develop confirmed disease progression per local assessment guidelines should be discontinued from the study. Pembrolizumab may be continued as a single agent if SD-101 is discontinued per investigator decision as described in Section 9.2. Patients who discontinue pembrolizumab must discontinue SD-101.

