Appendix 7: Imaging Modalities161

Appendix 8: ECOG Performance Status Index163

PROTOCOL SYNOPSIS

Objectives: **NOTE: As of Amendment 9, Phase 1 of the trial is complete. For Phase 2, efficacy and exploratory objectives will not be pursued.**

Phase 1 (Dose Escalation: Metastatic Melanoma)

Primary Objectives

- To assess the safety and tolerability of escalating doses of intratumoral SD-101 in combination with intravenous pembrolizumab in patients with metastatic melanoma
- To evaluate the expression of interferon (IFN)-inducible genes in whole blood 24 hours after intratumoral injection of SD-101 given with pembrolizumab in patients with metastatic melanoma as a pharmacodynamic marker of SD-101 activity
- To determine a recommended Phase 2 dose (RP2D) of SD-101 in combination with pembrolizumab to be evaluated in Phase 2

Exploratory Objectives

- To assess the preliminary response both locally and systemically including:
 - Treatment response of the injected Lesion A (local response)
 - Treatment response of the non-injected lesion(s) (systemic response)
 - Treatment response of all lesions
 - Time to response
- To assess changes in tumor biomarkers

Phase 2 (Dose Expansion: Metastatic Melanoma or Recurrent or Metastatic Head and Neck Squamous Cell Carcinoma)

Primary Objectives

- To assess the tumor response both locally and systemically including:
 - Treatment response of the injected lesion(s) (local response)
 - Treatment response of the non-injected lesion(s) (systemic response)
 - Treatment response of all lesions

Secondary Objectives

- To assess the safety and tolerability of SD-101 in combination with pembrolizumab

- To assess the time frame of tumor responses:
 - Time to response
 - Duration of response
- To assess progression-free survival (PFS)

Exploratory Objectives

- To assess changes in tumor biomarkers
- To identify and assess changes in potential tumor neoantigens in patients with recurrent or metastatic head and neck squamous cell carcinoma (HNSCC)
- To evaluate the expression of IFN inducible genes in whole blood 24 hours after intratumoral injection of SD-101 given with pembrolizumab in patients with recurrent or metastatic HNSCC as a pharmacodynamic marker of SD-101 activity

[figure not shown]
Trial Design: **NOTE: As of Amendment 9, Phase 1 of the trial is complete. Phase 2 of the trial has been modified to continue dosing per protocol; however, efficacy and exploratory endpoints will no longer be collected.**

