8.3 Biomarker Analysis

NOTE: As of Amendment 9, this section is no longer applicable.

Biopsies of Lesion A and 1 or more other accessible lesions will be analyzed for changes in correlative biomarkers (changes over time relative to baseline) including tumor-infiltrating lymphocytes and PD-L1 expression.

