10.1.2 Tumor Biopsy

Tumor biopsies from Lesion A (the target lesion to be injected) are required at Screening within 28 days prior to the first dose of SD-101. Two samples are required. The 2 samples can be taken as a single biopsy split into 2 samples or 2 separate biopsies and must meet the minimal sample size requirement per the study laboratory manual (ie, a minimum of 4 to 6 mm specimen, obtained via punch, core needle [14 gauge or smaller gauge needle], or surgical excision). One sample is for determining the expression level of PD-L1, and the other sample is for RNA expression profiling. The PD-L1 expression could be from an archival tissue sample of the target lesion if collected within 3 months of screening. A fresh biopsy needs to be obtained for the RNA profiling.

Subsequent tumor biopsies, which are taken after the start of study treatment, are obtained at time points specified per the schedule of trial events ([Appendix 1](#) through [Appendix 4](#)) and are collected pre-injection on treatment days or within the visit window. Two samples are required for these subsequent biopsies. A single biopsy can be split into 2 samples or 2 separate biopsies can be collected. Biopsies are required to meet the minimal sample size as indicated in the study laboratory manual. One sample will be used for immunohistochemistry and the second sample will be used for RNA expression profiling to identify and assess changes in immune cells and gene expression responses in the tumor microenvironment. Lesion A should be of a sufficient size such that the intratumoral biopsy does not compromise the investigator's ability to assess the lesion size changes per RECIST over time. If Lesion A is completely regressed, subsequent replacement lesion(s) do(es) not need to be biopsied. For Lesion A, biopsies would not be done in cases where it is judged by the investigator and in consultation with the Dynavax Medical Monitor to be not appropriate or feasible for either medical or technical reasons.

Written patient consent is required for biopsies. Tumor biopsies may be obtained via punch, core needle, or surgical excision. Biopsies should be limited to readily accessible tumor lesions (eg, skin; peripheral lymph nodes). If a core biopsy is performed, a tissue cylinder should be obtained that has proper size for histological examination and biomarker analysis (eg, immunohistochemistry of PD-L1, PD-L2, and other immunological markers; ribonucleic acid

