NOTE: As of Amendment 9, Phase 2 of the trial has been modified to continue dosing per protocol; however, efficacy and exploratory endpoints will no longer be collected, and the collection of safety endpoints has been simplified. The final study visit will be the EOS/Safety Follow-up. All other procedures to monitor disease progression and safety should be performed at the investigator's discretion according to local standard of care; these data do not need to be collected on the CRE. This Schedule of Trial Events has been amended and assessments that are no longer required have been deleted.

Screening Through Day 358

Trial Period:	Screening	Trial Treatment																						
		(every week ± 1 day)					(every 3 weeks ± 3 days)					(every 3 weeks ± 3 days)												
Day:	-28 to -1 ^a	1	8	9 ^{b,cc}	15	22	29	43	64	85	106	127	148	169	190	211	232	253	274	295	316	337	358	
Study Procedures																								
Informed consent	X																							
Inclusion/Exclusion Criteria	X																							
Demographics/Medical history/Prior medications ^g	X	X																						
Vital signs ^h	X	As of Amendment 9, per local standard of care at the discretion of the investigator.																						
Physical examination ⁱ	X																							
ECOG Performance Status	X																							
12-Lead ECG ^j	X																							
Review AEs ^k		X	X	X	X	X		X	X	X	X	X	X	X	X	X	X	X	X	X	X	X	X	
Review SAEs	X	X	X	X	X	X		X	X	X	X	X	X	X	X	X	X	X	X	X	X	X	X	
Concomitant medications ^l	X	X	X	X	X	X		X	X	X	X	X	X	X	X	X	X	X	X	X	X	X	X	
HIV, HPV status, and hepatitis testing ^m	X																							

APPENDIX 4: SCHEDULE OF TRIAL EVENTS (PHASE 2 EXPANSION COHORTS 5 AND 6 [ANTI-PD-1/L1 NAÏVE] AND COHORTS 7 AND 8 [ANTI-PD-1/L1 REFRACTORY OR RESISTANT]) (CLOSED) (CONT'D)

Screening Through Day 358 (Cont'd)

Trial Period:	Screening	Trial Treatment																					
		(every week ± 1 day)					(every 3 weeks ± 3 days)					(every 3 weeks ± 3 days)											
Day:	-28 to -1 ^a	1	8	9 ^{b, ee}	15	22	29	43	64	85	106	127	148	169	190	211	232	253	274	295	316	337	358
Serum chemistry and CRP ⁿ	X	X	X		X	X		X	X	X	X	X	X	X	X	X	X	X	X	X	X	X	X
Hematology ^o	X	As of Amendment 9, per local standard of care at the discretion of the investigator.																					
Coagulation ^p	X																						
Thyroid function tests ^q	X																						
Urinalysis with microscopy																							
Pregnancy testing ^r	X																						

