APPENDIX 1-4 FOOTNOTES (CONT'D)

Diary card issuance and/or review ^{bb}	Prior to each of the first 4 initial weekly doses of SD-101 in Phase 1, patients will receive a new Diary Card with instructions to measure and record local injection- site reactions and solicited AEs that occur post SD-101 injection. Note that injection-site reactions are not required to be recorded separately on the AE eCRF unless the duration is greater than 7 days. The completed Diary Cards will be reviewed with the patients at their next study visit.
SD-101 Post-treatment observation (minimum 90 minutes) ^{cc}	Patients will remain in clinic for 90 minutes after each of the first 4 weekly SD-101 injections in their first course and for 30 minutes after subsequent injections.
Tumor biopsies (consent required) ^{dd}	
Tumor biopsy of Lesion A will be performed within 28 days prior to the first dose of SD-101. Two samples are required at each time point. See specific guidance for samples in Section 10.1.2. Lesion A should be of a sufficient size such that the intratumoral biopsy does not compromise the investigator’s ability to assess the lesion size changes per RECIST over time. Biopsies may be obtained via punch, core needle, or surgical excision. Biopsies should be limited to readily accessible tumor lesions (eg, skin; peripheral lymph nodes). (See specific guidance for minimum needle gauge in the Study Reference Manual). Collections are to be done pre- injection on treatment days and may occur pre-injection on treatment days or within the visit window prior to treatment. Repeat samples may be required if adequate tissue is not provided. Details of tumor biopsy procedures including processing and shipping are provided in the study laboratory manual. Biopsies will be collected on:
 
 • Phase 1 Dose Escalation Cohorts 1-4 only: Screening, Days 29, 85 and 169 visits. • Phase 2 Dose Expansion Cohorts 1 and 3 only: Screening, Days 50, 106, and Day 190 visits. • Phase 2 Dose Expansion Cohorts 2 and 4 to 8 only: Screening, Days 29, 85, and Day 169 visits.
Day 9 and Day 30 visits ^{ee}	These visits are for HNSCC patients in Phase 2 Dose Expansion: Cohort 3 on Day 30, and Cohorts 4, 6 and 7 only on Day 9.

APPENDIX 5: TOXICITY GRADING SCALE FOR HEALTHY ADULT AND ADOLESCENT VOLUNTEERS ENROLLED IN PREVENTIVE VACCINE CLINICAL TRIALS

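### Amendment 9 ends the Phase 2 biomarker work, but the protocol still requires on-treatment Lesion A biopsies from any patient who has not passed the last biopsy day

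*Protocol*

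**What the plan says.** **What Amendment 9 switches off.** The Synopsis (Objectives) states: "For Phase 2, efficacy and exploratory objectives will not be pursued". Section 4.3.2.3, which lists the Phase 2 biomarker endpoints, is headed as no longer collected. Section 8.3 opens with "NOTE: As of Amendment 9, this section is no longer applicable", and the note to Section 10.7 does the same for expression profiling, neoantigen and mutational analysis, and HPV status. Section 12.0 repeats that exploratory objectives are dropped.

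**What remains as an instruction.** Section 4.1.4 carries an Amendment 9 note ending "This section has been modified accordingly". Below that note it says "Repeat tumor biopsies will be conducted for all Cohorts" and "Biopsies from Lesion A are required". The Synopsis (Other Assessments) also keeps tumor biopsies at the scheduled visits, under its own Amendment 9 note. Section 10.1.2 adds, for samples taken after treatment starts: "Two samples are required for these subsequent biopsies". The biopsy row is still in Appendices 2, 3 and 4, and footnote dd gives the days, for example "Phase 2 Dose Expansion Cohorts 2 and 4 to 8 only: Screening, Days 29, 85, and Day 169 visits".

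**How sites are told to read the schedule.** The note at the head of Appendices 2, 3 and 4 says: "This Schedule of Trial Events has been amended and assessments that are no longer required have been deleted". Section 10.0 makes the tests in the schedule the required ones and leaves all others to the investigator.

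**The concern.** A site that follows the amended text exactly would take repeated punch, core or excisional samples from a tumor under injection, for a purpose the same document has abandoned. That is procedural risk to the patient with no scientific return under the protocol. A site that sensibly omits the biopsy would depart from the protocol as written, and Section 12.9 requires deviations to be recorded. The protocol gives the site no means of deciding which instruction governs.

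No retained endpoint is biased by this. What is at stake is participant burden and an internally consistent protocol.

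**Working it through.** The plan gives no figure to reproduce. The check sets each stated use of on-treatment tissue against its status under Amendment 9, then counts what the surviving text requires.

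**Is any use left?**

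| Use of on-treatment tissue | Where stated | Status under Amendment 9 |
|---|---|---|
| Immunohistochemistry, RNA profiling | 10.1.2 | 8.3 and 10.7.1 not applicable |
| Mutational load, neoantigens (HNSCC) | 10.1.2 | 10.7.2 not applicable |
| Phase 2 biomarker endpoints | 4.3.2.3 | No longer collected |
| Replacement of patients lacking a post-baseline biopsy | 7.8 | Not applicable |
| Retained Phase 2 endpoint (injection-site reactions, AEs, SAEs) | 4.3.2.2 | Active, but uses no tissue |
| Treatment stopping decisions | 7.6, 9.2 | Active, but use no tissue |

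The PD-L1-negative subgroup of Cohort 1 (12.2) is defined at baseline, so it does not need on-treatment samples either.

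**Is there a waiver for loss of purpose?** Section 4.1.4 excuses regressed lesions. Section 10.1.2 excuses regression, biopsies that the investigator and Medical Monitor consider unsuitable or impracticable on medical or technical grounds, and potential safety risk. Written consent is also required. None of these releases a patient because the analysis has been dropped.

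**Requirement per patient** (days from footnote dd):

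- Cohorts 2 and 4 to 8: Days 29, 85 and 169, so 3 time points.
- Cohorts 1 and 3: Days 50, 106 and 190, so 3 time points.
- Samples: 3 × 2 = 6. Because one biopsy may be split into two samples (10.1.2), this means between 3 and 6 procedures.

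For a patient on the Day 29/85/169 schedule, the remaining requirement when Amendment 9 took effect is:

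- before Day 29: 3 time points, 6 samples
- after Day 29 and before Day 85: 2 time points, 4 samples
- after Day 85 and before Day 169: 1 time point, 2 samples
- after Day 169: none

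**Window of exposure.** 169 − 1 = 168 days, or 24 weeks from Day 1. For Cohorts 1 and 3, 190 − 1 = 189 days, or 27 weeks.

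**Who could be in it.** Table 4-1 shows Cohorts 1 to 4 closed to enrollment at Amendment 6 and Cohorts 5 and 6 at Amendment 8. Cohorts 7 and 8 were open at Amendment 8 and closed at Amendment 9. Their planned enrollment is 25 + 50 = 75. That is a planning figure for the two cohorts, not a count of patients still inside the window. Phase 1 is complete, so the reference to all cohorts has no effect there.

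**The case against.** **The documents do not agree that the tissue is useless.** The Synopsis (Analyses) keeps a summary of changes in tumor-infiltrating lymphocytes and gene expression, and Section 12.3.3 still describes biomarker endpoints. SAP Section 4.0 lists the Phase 2 biomarker changes without marking them as not implemented, and SAP Annex 1 promises a biomarker report. This stands as far as it goes: a reader might infer that no analysis of tumor tissue is planned anywhere, and that is too strong. But SAP Section 1.0 ties the SAP to Amendment 8, and tissue already collected can supply any such report. None of this text supplies a reason to take new biopsies after Amendment 9.

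**Surviving rows are not proof of a live requirement.** Appendices 2 to 4 also keep consent, eligibility and other Screening entries although enrollment is closed. That is fair, and it weakens any claim that a site has only one possible reading. The cases differ, though. A Screening entry cannot be acted on for an enrolled patient, whereas an on-treatment biopsy can. Sections 4.1.4 and 10.1.2 also state the requirement in words.

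**The 24-hour HNSCC visits look redundant too.** A reader might infer that the Day 9 and Day 30 columns and footnote ee should go as well, since Section 10.5 is no longer applicable. The documents do not support this. Those columns still carry AE, SAE and concomitant-medication review, which feed the retained safety endpoint.

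**Conclusion.** The contradiction is real and lies in current protocol text. Amendment 9 removes every Phase 2 protocol use of on-treatment tissue but leaves the biopsies required at up to 3 time points, with 2 samples each, and no waiver for loss of purpose.

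The practical reach is limited. It concerns only patients who had not passed Day 169 (Day 190 in Cohorts 1 and 3) when Amendment 9 took effect. The text available for review does not date Amendment 9 or say how many patients were in that window. That they would mainly be late entrants to Cohorts 7 and 8 is an assumption from the closing order in Table 4-1. Progression, discontinuation and lesion regression would reduce the number further, possibly to zero.

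A reader might infer that patients did undergo purposeless biopsies, or that about 75 patients each faced six procedures. Neither is supported: the documents show what is required, not what was done; 75 is planned enrollment; and three split biopsies satisfy the sample requirement. The point is worth correcting because the procedure is invasive and the correction is easy, not because any result is compromised.

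**What to change.** Choose one of two consistent positions.

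1. **No new tissue.** Remove the on-treatment biopsy entries from Appendices 2 to 4 and the Phase 2 on-treatment days from footnote dd. State in the Synopsis (Other Assessments) and Sections 4.1.4 and 10.1.2 that, as of Amendment 9, no further Phase 2 research biopsies are taken.
2. **New tissue is wanted.** Reverse the Amendment 9 notes at Sections 4.3.2.3, 8.3 and 10.7, and state which analysis is retained.

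Under the first option, also reconcile the leftover biomarker text in the Synopsis (Analyses), SAP Section 4.0 and SAP Annex 1 by limiting it to tissue already collected. Under either option, keep the Day 9/Day 30 visit column and footnote ee.

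The cost is wording in the next amendment or an administrative letter to sites. Under the first option no endpoint retained by Amendment 9 loses data, and site and laboratory work falls.
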